## 2.3 Survival Results of Standard Treatment

The outcome according to a multiinstitutional database of 888 consecutive patients undergoing cystectomy and lymphadenectomy for bladder cancer revealed a mean recurrence-free and bladder cancer specific survival of 58% and 66%, resp. at 5 years (12). The recurrence-free and overall survival in a large single centre study of 1,054 male and female patients was 68% and 66% at 5 years and 60% and 43%, at 10 years, respectively (5). In node positive patients, 10-year disease-specific and overall survival rates in another study have been reported to be 27.7% and 20.9% respectively (13). In this cohort, 10-year disease-specific and overall survival rates were 72.9% vs. 49.1% for organ confined (defined as < pT3a), and 33.3% vs. 22.8% for non-organ confined disease (13). In another study, 5-year recurrence-free survival was 76% in patients with pT1 tumours, 74% for pT2, 52% in pT3, and 36% in pT4 tumours (14). Tumour stage and nodal involvement are the only independent predictors of survival (15).

Local recurrence accounts for about 30% of relapses, whereas distant metastases are more common. Before the development of effective chemotherapy, patients with metastatic urothelial cancer rarely exceeded the median survival of 3-6 months (16). Chemotherapy increases overall survival in patients with relapse after cystectomy or unresectable disease.

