#### **3.2 Secondary Objectives**

Secondary objectives are:

- To evaluate overall survival in the overall study population, in the subpopulations with and without use of neo-adjuvant chemotherapy and in the subpopulations with and without use of adjuvant chemotherapy
- To evaluate Disease-free (DFS) in the subpopulations with and without use of neo-adjuvant chemotherapy and in the subpopulations with and without use of adjuvant chemotherapy
- To evaluate Disease-free specific survival (DFSS) in the overall study population, in the subpopulations with and without use of neo-adjuvant chemotherapy and in the subpopulations with and without use of adjuvant chemotherapy
- To evaluate Distant metastasis-free survival (DMFS) in the overall study population, in the subpopulations with and without use of neo-adjuvant chemotherapy and in the subpopulations with and without use of adjuvant chemotherapy
- To evaluate the safety of recMAGE-A3 + AS15 ASCI in the overall study population, in the subpopulations with and without use of neo-adjuvant chemotherapy and in the subpopulations with and without use of adjuvant chemotherapy
- .
- Translational research:
  - a) To identify a gene signature predictive to recMAGE-A3+AS15 ASCI in MIBC.
  - b) To evaluate on exploratory basis a possible correlation between gene expression profile of the primary tumor and clinical efficacy of recMAGE-A3 + AS15 ASCI compared to placebo in terms of:
    - Disease-free Survival (DFS)
    - Overall survival

c) To evaluate expression of genes in a previously identified gene signature and evaluate their correlation with clinical efficacy of recMAGE-A3 + AS15 ASCI compared to placebo in terms of:

- Disease-free Survival (DFS).
- Overall survival.
- Disease-free specific survival (DFSS)
- Distant metastasis-free survival (DMFS).

d) To characterize of the tumor microenvironment and lymphocyte infiltration in the primary tumor and its recurrence lesions

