#### 6.1.2 Randomization and treatment allocation

As of 23 September 2014, the recruitment was put on hold (sites were still allowed until 3 February 2015 to randomize patients that signed the informed consent or were in the screening process). As of Protocol Amendment 4.0, the recruitment will be stopped and the study will be unblinded. For patients randomized to the placebo group, no further protocol visits will be performed except for the concluding visit and no further doses will be administered. Patients receiving active treatment (i.e. those patients not on placebo, and patients that have not already completed or interrupted their MAGE-A3 ASCI treatment) will be offered the option to continue the administration of the study treatment until the last dose is administered or until recurrence, whichever comes first, or until the patient or the investigator decides to stop the study treatment. Therefore, as of Protocol Amendment 4.0, the study will continue only with patients from the active treatment group who will decide to stay in the study. Treatment will not be possible anymore after November 2016. For the rationale see Section 2.6.2.

The aim is to start study treatment as soon as the patient is recovered from surgery or, for patients who receive adjuvant chemotherapy following surgery, the patient is recovered from chemotherapy. Randomization occurred maximally 13 weeks after cystectomy for patients not scheduled to receive adjuvant chemotherapy. For patients receiving adjuvant chemotherapy, the first study treatment administration must be given 3 - 6 weeks after the last day of chemotherapy administration and no more than 36 weeks after surgery.

Treatment allocation at the investigator site will be performed using a central system on Internet, initially used for randomization (SBIR; available 24H/day, 7D/week) which accounted for the following stratification factor: T category, Neo-adjuvant Chemotherapy vs. Adjuvant Chemotherapy vs no chemotherapy, and minimization factors the number (1, 2 vs. 3, 4) of cycles received (if peri-operative chemotherapy has been administered), N category, gender and centre. This randomization took place maximum 7 days before first study treatment administration at Visit 1.

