## **10. STATISTICAL CONSIDERATIONS**

### **10.1 Sample Size Calculation**

The assumptions for the sample size calculations were the following.

- Primary endpoint on which sample size is based is disease free survival (see Section 3.3)
- Hazard ratio of expected disease free survival of recMAGE-A3 + AS 15 ASCI treated patients relative to placebo treated patients that will be significant at the end of study is 0,75.
- Median Disease-Free Survival in the placebo groups is 24 months
- Recruitment period is 4-5 years
- All patients will be observed for a maximum of 5 years from their first study administration and with a minimum of 6 months after treatment completion.
- Null hypothesis H0: "there are no differences in expected disease free survival between the placebo treated patients and recMAGE-A3 + AS 15 ASCI treated patients.
- Alternative hypothesis H1: "the recMAGE-A3 + AS 15 ASCI treated patients have a different disease free survival compared to the placebo treated patients.
- Anticipated drop out percentage is 15 %
- One-sided alpha for final analysis is 0,05
- Power to detect a  $HR = 0,75$  is 50 %. Power to detect a  $HR = 0,65$  is 80 %.
- Randomization: 2 recMAGE-A3 + AS 15 ASCI patients versus 1 Placebo patient.
- Interim analysis planned when 65% of the total number of events have occurred.
- Calculations were done using East 5.3.

Based on these assumptions and in order to reach 155 events\* (see section 10.2), we needed a total of 273 patients for randomization. A total of 182 patients were to be randomized for treatment with recMAGE-A3 + AS 15 ASCI and 91 patients were to be randomized for treatment with placebo. Total number of evaluable patients (15 % drop out percentage) would be 231.

The power to detect a  $HR = 0,75$  (from 24 to 32 months) was 50%. The study would have 65% power if the true  $HR = 0,7$  (from 24 to 34 months) and 80% power if the true  $HR = 0,65$  (from 24 to 37 months).

Due to the Protocol Amendment 4.0, not all analyses described in this section will be performed and no interim analysis will be done. Please see Section 2.6.2 for the rationale.

\* 147 events without interim analysis

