### 10.3 Statistical Analyses

As of Protocol Amendment 4.0, statistical analyses will not be assessed as planned. All clinical data collected in the study will be analysed descriptively. Please see Section 2.6.2 for the rationale.

Patient characteristics, demographics and baseline measurements will be summarized in order to provide a characterization of the patient population. Descriptive statistics, e.g. mean, standard deviation, median, range, frequency distributions as appropriate will be presented for each randomization group: recMAGE-A3 + AS 15 ASCI versus the Placebo arm.

A yearly safety analysis will be performed until all patients have finished the treatment phase (Visit 14) which is 112 weeks after the last patient was randomized. The incidence and severity of all adverse events will be tabulated per treatment group. Treatment related toxicity > grade 2 will be descriptively described in both arms.

The description of the safety data will be performed, first globally then for each of the study arms. The safety analysis will be performed in all patients who are randomized and who received at least one Study Treatment Administration.

The efficacy analysis will be performed including all patients who are randomized and who received at least one Study Treatment Administration.

Disease free Survival (Section 3.3) will be estimated by means of the Kaplan Meier method and comparison between treatment groups will be done by means of the log-rank test.

A Cox proportional hazards model will be applied to correct for treatment effects and to assess the influence of prognostic and confounding factors such as T category, Neo-adjuvant Chemotherapy vs. Adjuvant Chemotherapy vs. no chemotherapy, N category, gender, centre, multifocality of bladder carcinoma (Y/N), age (continuous), presence of Carcinoma in Situ (CIS) and gene profile population.

The analyses of other outcome measurements will be analyzed in an exploratory way with methods appropriate for the type of the variable. Both the safety data and the efficacy data will be summarized by appropriate descriptive statistics.

For each patient entering, the reason for discontinuation (e.g. patient decision, urologists decision, lack of efficacy, adverse events) should be clarified. The description of the reason for discontinuation will be performed.

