All tests of efficacy hypotheses based on between-treatment comparisons will be performed at the 5% level of significance, and will be two-sided. Statistical tests based on within-treatment comparisons will be performed at the 5% level of significance and will be two-sided. No adjustments will be made to nominal significance levels to account for multiple comparisons made on the same data.

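### The DFS log-rank test names no strata although randomization was stratified: about 5 points of two-sided power at the planned size, 0 to 2 points now

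*Combined protocol and SAP*

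**What the plan says.** Section 6.1.2 describes central allocation using "stratification factor: T category, Neo-adjuvant Chemotherapy vs. Adjuvant Chemotherapy vs no chemotherapy, and minimization factors", the latter being number of chemotherapy cycles, N category, gender and centre. Section 10.3 estimates DFS by Kaplan-Meier and says that "comparison between treatment groups will be done by means of the log-rank test". It does not call the test stratified or unstratified. The next paragraph adds a Cox model to assess prognostic and confounding factors. Its list is open-ended and includes T category, the three-level chemotherapy factor, N category, gender and centre. The section does not say which of the two analyses decides the comparison of arms.

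On prognosis, section 2.3 reports that "5-year recurrence-free survival was 76% in patients with pT1 tumours, 74% for pT2, 52% in pT3, and 36% in pT4 tumours". On error rates, section 10.1 says "One-sided alpha for final analysis is 0,05", while section 10.3 says "All tests of efficacy hypotheses based on between-treatment comparisons will be performed at the 5% level of significance, and will be two-sided".

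Section 10.3 also opens by stating that, as of Amendment 4.0, the analyses will not be done as planned and all clinical data will be analysed descriptively. Section 5.1 gives 83 of 273 patients randomized when recruitment was put on hold.

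**The concern.** Stratified allocation removes chance imbalance between arms on the stratifying factors. If those factors are prognostic, an unstratified log-rank test still carries the between-stratum variation in its variance estimate, so its true size falls below nominal. Pooling strata with different baseline hazards also pulls the overall hazard ratio towards 1 relative to the within-stratum effect. Both mechanisms cost power. The loss is avoidable, because the factors were entered for every patient at randomization.

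**Working it through.** **1. The plan's own figures.** Schoenfeld's formula with 2:1 allocation is d = (z_alpha + z_beta)^2 / [p(1-p)(ln HR)^2], with p(1-p) = 2/9. At HR 0.65, one-sided 0.05 and 80% power:

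(1.645 + 0.842)^2 / [0.2222 x 0.1856] = 150 events, against the stated "147 events without interim analysis".

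Power at 147 events is Phi(sqrt(147 x 2/9) x |ln HR| - z_alpha). This gives 79.3%, 65.3% and 50.0% at HR 0.65, 0.70 and 0.75; the plan states 80%, 65% and 50%. So the sample size is an ordinary unstratified, one-sided calculation. Under the two-sided 5% rule, the same 147 events give 69.2% at HR 0.65. That drop is a separate conflict between sections 10.1 and 10.3 and is not part of the loss measured below.

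**2. Prognostic strength of T.** Assuming exponential times, the hazards are proportional to -ln(0.74) = 0.301, -ln(0.52) = 0.654 and -ln(0.36) = 1.022 for pT2, pT3 and pT4. The ratios are 1 : 2.17 : 3.39. The documents give no hazard ratio for chemotherapy type and no stratum proportions.

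**3. Simulation, common set-up.** 273 patients, 147 events, 2:1 blocks within strata, 54-month accrual (section 10.1 gives 4-5 years), 15% dropout, pooled placebo median 24 months, and HR 0.65 applied within strata. The T2/T3/T4 mixes are assumptions. Differences come from unrounded values.

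*Stratifying the test by T category alone* (6,000 trials per scenario; mixes 40/45/15 and 55/35/10; 30% node-positive; no chemotherapy effect):

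| Test | Scenario | Unstratified | Stratified by T | Gain (points) |
|---|---|---|---|---|
| Two-sided 5% | N not prognostic | 65.8%, 66.2% | 71.0%, 71.7% | 5.2, 5.5 |
| Two-sided 5% | N+ HR 2 | 63.6%, 62.7% | 68.4%, 67.8% | 4.9, 5.1 |
| One-sided 0.05 | all of the above | | | 3.6 to 4.1 |

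A repeat run gave 66.4% to 71.5% and 65.9% to 70.9% two-sided, and 3 to 4 points one-sided. Two-sided size at HR 1 was 3.7-4.2% unstratified and 4.6-5.4% stratified.

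*Stratifying the test by all T x chemotherapy cells*, one-sided 0.05 (8,000 trials per scenario):

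| Prognostic effect assumed | Unstratified | Stratified | Gain (points) |
|---|---|---|---|
| None | 81.1% | 79.5% | -1.5 |
| Weak T (1/1.5/2) | 80.1% | 79.8% | -0.3 |
| Section 2.3 T effect, mix 40/45/15 | 76.4% | 79.1% | +2.7 |
| Section 2.3 T effect, mix 30/50/20 | 77.0% | 79.0% | +2.0 |
| Section 2.3 T effect plus chemotherapy HR 2 | 74.5% | 79.2% | +4.7 |
| Section 2.3 T effect plus chemotherapy HR 3 | 70.5% | 79.2% | +8.6 |

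One-sided size with the section 2.3 T effect alone was 4.3-4.8% unstratified.

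**4. Reading the two tables together.** On the section 2.3 T effect alone, the gain is about 5 points two-sided. One-sided it is 2 to 4 points: the lower part comes from stratifying on every cell, the upper part from T alone. If nothing is prognostic, stratifying by T alone cost under 1 point in the repeat run, and stratifying by all cells cost 1.5.

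**5. Truncated trial.** At an assumed 87 patients and 23-26 events (the documents give 83 randomized at the hold and allow later randomization of patients already in screening), stratifying by T adds 0 to 2 points. Stratifying by all nine T x chemotherapy cells at that size lost about 1 point at HR 0.5, because the cells are too thin.

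**The case against.** The strongest objection is that this analysis has been overtaken. Amendment 4.0 makes the reporting descriptive, and the planned 147 events will not be reached. That stands, and it takes most of the practical weight off the point. What remains is that section 10.3 keeps the log-rank, Cox and two-sided testing sentences, so it is unclear what test or hazard ratio, if any, will be reported.

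Second, the Cox model already contains both stratifying factors. That is true, and no unadjusted hazard ratio is planned, so a reader should not infer that an attenuated one would be published. But the model's covariate list is open, it includes centre across 50 sites, and it is not named as the comparison of arms.

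Third, section 10.1 expresses HR 0.65 as a shift in whole-group medians from 24 to 37 months, which reads as a marginal effect. On that reading the unstratified test already has its planned power, and stratifying is a gain on top. This is why the size of the loss is conditional.

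Fourth, the section 2.3 rates are not restricted by nodal status, while T4 patients are eligible only if N0. The pT4 ratio of 3.39 may therefore be too high for this population, and adding an N+ effect to those rates risks double counting. The gain would then be somewhat smaller; its direction depends on T still being clearly prognostic.

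**Conclusion.** The mismatch between stratified allocation and a log-rank test with no stated strata is real but minor. The size is about 5 points of two-sided power, or 2 to 4 points one-sided, at 147 events, with two-sided size about 4% instead of 5%. This rests on the section 2.3 T effects, assumed stratum mixes, proportional hazards and a within-stratum HR of 0.65. In the trial as it now stands, it is about 0 to 2 points.

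Three stronger readings are not supported:

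- **A loss as high as 7 points at the planned size.** One-sided with all cells stratified, even 4.7 points needed an assumed chemotherapy hazard ratio of 2, which appears nowhere in the documents. Two-sided, the T figures alone stop at about 5.5.
- **An invalid test.** The deviation is conservative when strata are prognostic; the false-positive rate is not inflated by it.
- **Erroneous chemotherapy subgroups.** Section 3.2 asks for results "in the subpopulations with and without use of neo-adjuvant chemotherapy and in the subpopulations with and without use of adjuvant chemotherapy". Patients without chemotherapy fall in both "without" groups, but these are two legitimate one-way splits, each answering its own question.

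**What to change.** In section 10.3, state that any log-rank test or hazard ratio still reported for DFS is stratified by T category, and that chemotherapy type enters the Cox model as a covariate at its three randomized levels (neo-adjuvant, adjuvant, none). Do not stratify by all T x chemotherapy cells at the truncated size.

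This costs one sentence and no new data, since both factors were recorded at randomization. The statistical downside is about 1 point of power or less if T category turns out not to be prognostic. Reporting chemotherapy subgroups by the three disjoint levels, alongside the planned splits, is an optional addition that suits a descriptive report.

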## 11. ETHICAL CONSIDERATIONS

### 11.1 Regulation Statement

This study will be conducted according to the principles of the Declaration of Helsinki (see for the most recent version: [www.wma.net](http://www.wma.net)) and in accordance with the European and local regulations and applicable guidelines.

### 11.2 Recruitment / Consent and Ethical Review Procedure

Eligible patients will be fully informed by the principal investigator (PI), the local investigator and/or the local research coordinator and his research staff, whatever is applicable, about the study and asked to participate. The patient will receive a patient information sheet and will have ample opportunity to ask any question he/she might have. He/she will have sufficient time to consider the study's implications before deciding to participate in the study. Patient's consent will be noted on an informed consent form (ICF).

If during the study the patient for whatever reason no longer wishes to participate he/she can withdraw his/her consent at any time, without any further consequences regarding their treatment.

Submission of the protocol and any protocol amendments to regulatory agencies will occur in accordance with local regulatory requirements.

Prior to the start of the study, in some countries, the protocol has to be approved by one recognized medical ethics review committee for all participating institutions (the accredited review committee). The EC shall form a conclusion on the scientific and medical-ethical aspects of the protocol. If the EC requires further information to form its decision or believes the protocol needs to be adjusted, it shall inform the PI or the Sponsor immediately. On the basis of the additional information or the adjusted protocol, the EC shall reach its conclusion about whether or not the protocol is acceptable in terms of the research's scientific and medical-ethical aspects. Approval will be indicated in writing with reference to the final protocol number, version and date. The use of medication as described in this protocol must not under any circumstances deviate from the agreed protocol. In exceptional circumstances, for example when the health of the subjects is at risk, the investigator can use his clinical judgement and alterations may be made. The event must then be documented in detail to the Sponsor and, if applicable, the EC and the PI and the investigators should be notified. If in the opinion of the local investigator or the PI the clinical observations in the study suggest it may be unwise to continue, they will be able to terminate the study locally or entirely, respectively. If it becomes apparent that patient enrolment is unsatisfactory or the quantity or quality of the data received is inaccurate or incomplete on a chronic basis, the PI has the right to terminate the study.

and remove all study equipment from the investigational site. If the study is stopped early the EC should be informed about the reasons.

### **11.3 Benefit and Risks Assessment**

Given the situation of the patient who needs a cystectomy, the extra burden and risks associated with participation in the study is considered minimal and acceptable. During the first 3 months in the study, the number of patient visits is higher. This is due to the need for administration of treatment every 3 weeks. Hereafter, the number of visits and treatments is equal to what patients with these criteria is offered when they are treated in the standard way, which is watchful waiting after cystectomy. Possible extra procedures in this study depend on local routine practices. For example 3-monthly CT scans /MRI's can be extra if 6-monthly imaging procedures are considered standard routine practice (during treatment phase only). Also laboratory assessments and the questionnaire on smoking habits can be considered as extra. The risks related to the expected treatment outcome, quality and quantity of side effects of the study medication can be considered as acceptable (see Section 2.5.3). Benefit for the patient is that the patient is followed according to the latest standards and guidelines of treatment of MIBC and the patient has a chance on early detection of recurrence of disease.

### **11.4 Compensation for Injury**

The Sponsor will arrange a liability insurance which is in accordance with GCP and local legal requirements.

## 12. ADMINISTRATIVE ASPECTS AND PUBLICATION

### 12.1 Study Organisation & Management

For this multicentre study, an initiating investigators meeting at a central location will be held to standardize data management procedures and resolve questions regarding protocol conduct. At the initiation meeting, the investigator and eventual other site study personnel will be instructed how to conduct the study- and data management procedures. In addition, the sites will be able to download the required materials via the EAU RF website. EAU RF's representatives will conduct field data review periodically. It is the responsibility of EAU RF's representatives to verify adherence to the protocol and the completeness, accuracy and consistency of the data. The investigator or a qualified employee will enter all relevant data into eCRF's, in accordance with the instructions provided. The investigator may be requested to provide a copy of the applicable pathology or radiology reports. These copies will be used as source verification. An explanation for the omission of any required data should appear on the appropriate e-page. The investigator must sign an agreement thereby stating that she/he takes responsibility for the accuracy of the data in the entire eCRF.

Original subject records (e.g., hospital charts, clinical records, laboratory printouts) should be available at each study site for source document review by EAU RF's representatives. Source document review is the cross checking of information recorded on eCRF's with that recorded in the original subject records. It is not the purpose of source document review to ensure that all information in the eCRF is also recorded elsewhere in the subject's records; the purpose is to help ensure that the eCRF accurately reflects information generated during the study. In this study, source document review of specific types of information will be conducted in all patients enrolled. EAU RF's representatives ensure the privacy of the patient data by only collecting the patient data without the patient details that could identify the individual patient. The investigator should give the monitor access to all relevant patient data.

Queries to be issued to the investigator will consist of questions to clarify for instance missing data, inconsistencies, illegible data, illegal values and items that are not clearly corrected.

When all patient and visit data are received at EAU RF, all data problems have been resolved, all data checks and quality control checks have been performed, the study database is considered to be clean and can be locked. This cleaning and locking process will be performed on a per patient and per visit basis. In addition, the study centre may be audited in depth for study quality assurance by EAU RF representatives, and/or inspected by a national regulatory authority. This audit may include review of all source documents, drug records, original clinic case-notes, some or all of the

facilities used in the trial, etc. Patient confidentiality will be maintained at all times and consent for this will be obtained prior to entry of the patient into the clinical trial.

